For this reason, considering the potential beneficial effects of ICS in this population, we propose to conduct a real-life study in which we will randomize elderly frail, multimorbid COPD patients recently hospitalized due to AECOPD to one of two regimens: 1) usual and optimized treatment for concomitant chronic diseases plus LABD but no ICS, and 2) usual and optimized treatment for concomitant chronic diseases plus LABD+ICS. The choice of the particular LABD and ICS will be left to the discretion of the clinical investigator. Thus, the proposed study will be a real-life but randomized study with a 12 month treatment period and 3 months follow-up. All diagnostic procedures and medical treatments will be performed according to best medical practice (PDTA) which is usually based on the most recent and credited international guidelines for both of these chronic diseases, e.g., European Society of Cardiology (ESC) guidelines for cardiac diseases (www.esc.org) and GOLD guidelines (www.goldcopd.org) for COPD.

2.1. Study Rationale

Re-hospitalizations and death are major concerns for patients hospitalized due to AECOPD. By limiting this study to include only patients admitted to the hospital because of exacerbation of respiratory symptoms and discharged with the DRG 087 (pulmonary edema or respiratory failure), we are referring to a population that in 2014 accounted for about 139,000 hospitalizations in Italy (Vestbo et al 2016(b), Ministero della Salute www.salute.gov.it). Many AECOPD may also be included in other DRG codes, such as DRG 127 (cardiac failure and shock, 190,000), DRG 89 (pneumonia, 73,000), DRG 125 (other cardiovascular diseases, 63,000) and DRG 088 (COPD, 42,000) (Roca et al 2013, Vanfleteren et al 2016).

The reason why AECOPD are coded as DRG 087 and not DRG 088 (COPD) is administrative, as reimbursement is much higher if COPD patients are admitted for respiratory failure than for stable disease. In the last 15 years there has been a significant decrease in admissions with DRG 088 and a simultaneous increase in DRG 087.

Compared to randomized clinical trials conducted in younger patients with milder cases of COPD (Calverley et al 2007, Vestbo et al 2016(a)), meta-analyses and registry studies suggest that, while new initiation of LABAs or LAMAs in patients with COPD is associated with an increased severe cardiovascular risk (Wang et al 2018) particularly in the elderly (Gershon et al 2013), long-acting bronchodilators plus inhaled steroids (LABD+ICS) reduce hospitalizations and mortality in elderly, frail patients (Macie et al 2006, Sin et al 2005, Gershon et al 2014) with COPD.

For GOLD D patients, GOLD recommends LABD either alone (LAMA or LABA) or in combination (LAMA+LABA), mainly to reduce symptoms and exacerbations (Wedzicha et al 2016). GOLD also recommends adding ICS to LABD, but only if patients are young and/or have eosinophilia and/or a history of asthma, mainly because LABA+ICS is the most prescribed treatment in these patients.

We speculated that elderly COPD patients recently hospitalized due to AECOPD may have fewer re-hospitalizations and increased survival in the following year if treated with LABD+ICS rather than with LABD alone.

The aim of this study is to examine the efficacy and safety of currently recommended and prescribed inhalation therapies to elderly, frail and multimorbid COPD patients with a recent hospitalization due to an AECOPD. The study involves a group of patients who have never before been selected for a clinical trial and who represent the 5th most common cause of hospitalization and the 3rd most common cause of death in Italy.

2.2. Background

For GOLD D patients, GOLD recommends LABD either alone (LAMA or LABA) or in combination (LAMA+LABA), mainly to reduce symptoms and exacerbations (Wedzicha et al 2016). GOLD also recommends adding ICS to LABD, but only if patients are young and/or have eosinophilia and/or a history of asthma, mainly because LABA+ICS is the most prescribed treatment in these patients.

We speculate that multimorbid elderly COPD patients recently hospitalized with an AECOPD and concomitant cardiovascular disease may have fewer re-hospitalizations and increased survival in the following year if treated with LABD+ICS rather than with LABD alone.

In this study patients will be randomised to one of two treatment regimens:

- 1) Usual and optimized treatment for concomitant chronic diseases plus LABD(s) but no ICS
- 2) Usual and optimized treatment for concomitant chronic diseases plus LABD(s)+ICS.

The choice of the particular LABD(s); (1 or 2) and ICS will be left to the discretion of the clinical investigator. Thus, the proposed study will be a real-life but randomized study with a 12 month treatment period followed by 3 months follow-up. All diagnostic procedures and medical treatments will be performed according to best medical practice (Percorsi Diagnostico Terapeutici Assistenziali (PDTA)) at the study centre. Best medical practice is usually based on the most recent and credited international guidelines for these chronic diseases such as the ESC guidelines for cardiac diseases (www.esc.org) and GOLD guidelines (www.goldcopd.org) for COPD.

2.3. Benefit/Risk Assessment

The key aim of this study is to examine the efficacy and safety of currently recommended and prescribed inhalation therapies to elderly, frail and multimorbid COPD patients with a recent hospitalization due to AECOPD. The study involves a group of patients who have never before been selected for a clinical trial and who represent the 5th most common cause of hospitalization and the 3rd most common cause of death in Italy.

The main objective of this study is to determine whether a long-term inhalation treatment including LABD(s) and ICS, that is currently recommended and shown to reduce symptoms and exacerbations, may also reduce re-hospitalizations and/or death in elderly, frail and multimorbid COPD patients with a recent hospitalization due to AECOPD.

Despite attempts to define the risk of re-hospitalization and death in this population, we could not go beyond an estimated re-hospitalization rate of 20% at 1 month in severe AECOPD (Shah et al 2016), and a re-hospitalization/death rate of 30% at 1 year (Tokgoz et al 2016). However, these estimates were obtained from retrospective studies reported in the literature (Shah et al 2016, Tokgoz et al 2016) that included patients with respiratory failure if they required non-invasive as well as invasive ventilation. In addition, as previously mentioned, the characterization of AECOPD in real life is quite inaccurate, not only as to the nature of the exacerbation of respiratory symptoms (Roca et al 2013) but also in confirming the diagnosis of COPD by spirometry.

For all these reasons, we estimated that by selecting patients with a diagnosis of COPD confirmed by spirometry, even if elderly, frail and with comorbidities, particularly the main chronic heart diseases (CHF, IHD, AF); excluding patients with respiratory failure requiring invasive mechanical ventilation, up to 20% of whom are expected to be re-hospitalized within the first month after a hospitalized AECOPD; and optimizing diagnosis and treatment at the beginning of the study, the rate of re-hospitalization or death will decrease to a maximum of 15% in patients treated with usual care plus LABD(s) but no ICS, whereas we expect that this number will decrease to 9% (40% reduction) by treating them with LABD(s)+ICS.

This reduction would be considered clinically relevant, a reduction of about 60 cases in the study that would translate to a hypothetical population of 100,000 similar patients in Italy, and a reduction of 6,000 hospitalizations/deaths in 1 year (Vestbo et al 2016(b), Ministero della Salute www.salute.gov.it).

In addition to the above-mentioned advantages, the study will provide a unique learning exercise for the 39 hospital centers planned to participate in the study, enabling them to improve their ability to characterize and treat this difficult population of patients who are often encountered not only in hospital pulmonary units but also in many hospital internal medicine units.

Since this will be a pragmatic real-life study, there are no anticipated additional risks to the standard medical procedures for patients who agree to participate in this study. The choice of the specific LABD(s) and ICS used to treat each patient will be left to the discretion of the clinical investigator, according to the ICS and LABD(s) treatments available in their pharmacy department.

More detailed information about the known and expected benefits and risks and reasonably expected adverse events of the study interventions may be found in the study Participant Information Sheet. Information may also be found in the Patient Information Leaflet and Summary of Product Characteristics for the specific licensed products prescribed for the individual participants.

3. Objectives and Endpoints

Objectives	Endpoints
Primary	

 to demonstrate that in elderly COPD patients with one or more cardiac comorbidities (heart failure, and/or ischemic heart disease, and/or atrial fibrillation) who have been recently hospitalized due to AECOPD, 1-years treatment with LABD+ICS will prolong the time to first re-hospitalization and/or the death for any cause when compared to 1-years treatment with LABD alone 	
 composite event of the time to first re-hospitalization and/or death (all cause)
Secondary	
 to compare the number of moderate/severe exacerbations of COPD in the two patient groups to compare the number of re-hospitalizations and deaths (all cause) in the two patient groups to compare quality of life (QoL) scores measured using the COPD Assessment Test (CAT) and mMRC dyspnoea scale between the two patient groups to verify if one year of treatment with combination therapy including ICS increases the risk of pneumonia to compare the number of acute cardiac events in this frail, elderly COPD population to compare the incidence of deaths due to cardiovascular events to compare changes in lung function 
 number of moderate/severe COPD exacerbations number of re-hospitalizations and deaths (all cause) QoL variation measured as change in CAT total score from baseline to end of treatment period. change in mMRC dyspnea score from baseline to end of treatment period. number of pneumonia events number of acute cardiac events number of cardiovascular deaths change in FEV1 from baseline to the end of treatment period change in FVC from baseline to the end of treatment period

4. Study Design

4.1. Overall Design

This will be a phase IV, open label, multicenter, randomized pragmatic study in frail elderly patients with COPD. Participants will be treated with either inhaled LABD alone or LABD combined with inhaled glucocorticosteroids. The choice of the specific LABD and ICS to be used will be left to the discretion of the clinical investigator, according to the treatments available from their pharmacy department.

The center will be considered as a unique stratifying factor, so the study will have a balanced-block center-stratified design.

The main aim of the study is to assess whether, in elderly patients with COPD and one or more cardiac comorbidities (heart failure, and/or ischemic heart disease, and/or atrial fibrillation) recently hospitalized because of an acute exacerbation of COPD, 12 months treatment with LABD(s)+ICS can increase the time to first re-hospitalization (all cause) and/or death for any cause when compared with LABD(s) alone. Patients will be followed-up for 3 months after completion of the 12 month treatment period.

4.2. Scientific Rationale for Study Design

This is a pragmatic, randomized, open study. Pragmatic studies are designed to evaluate the effectiveness of different treatment strategies in real-life clinical practice.

The key aim of this study is to examine the efficacy and safety of currently recommended and prescribed inhalation therapies to elderly, frail and multimorbid COPD patients with a recent hospitalization due to AECOPD. The study involves a group of patients who have never before been selected for a clinical trial and who represent the 5th most common cause of hospitalization and the 3rd most common cause of death in Italy. The main objective is to determine whether a long-term inhalation treatment including LABD(s) and ICS, can reduce re-hospitalizations and/or death in elderly, frail and multimorbid COPD patients with a recent hospitalization due to AECOPD.

The pragmatic study design means that the choice of the particular LABD(s) and ICS to be prescribed for each patient will be left to the discretion of the clinical investigator and all diagnostic procedures and medical treatments will be performed according to best medical practice at the study centre.

The randomized pragmatic design of this study will help to provide information about treatment choices in real clinical practice and the results will help physicians to make informed choices about the most appropriate treatments in frail elderly COPD patients with multiple comorbidities. The study will also provide a unique learning exercise for the study centers, enabling them to improve their ability to characterize and treat this difficult population of patients.

4.3. Justification for Dose

The choice of the specific LABD(s) and ICS used to treat each patient will be left to the discretion of the clinical investigator. All COPD treatments will be administered using licenced dosages.

4.4. End of Study Definition

A participant is considered to have completed the study if he/she has completed all phases of the study including the last visit (Visit 7).

The end of the study is defined as the date of the last visit of the last participant in the study.

5. Study Population

Prospective approval of protocol deviations to recruitment and enrollment criteria, also known as protocol waivers or exemptions, is not permitted.

5.1. Inclusion Criteria

Participants are eligible to be included in the study only if all of the following criteria apply:

Age

1. Participant must be older than 60 years of age, at the time of signing the informed consent.

Type of Participant and Disease Characteristics

2. Recently (within 6 months) discharged from hospital with a diagnosis of acute exacerbation of COPD (usually coded as DRG 087 or DRG 088).
3. Participants with a clinical diagnosis of COPD (i.e. previous diagnosis of COPD and/or treatment with short acting bronchodilators (SABD), LABD or LABD+ICS
4. Spirometry confirmed diagnosis of COPD, post-bronchodilator (30 minutes after 400 µg salbutamol) FEV1/FVC ratio <0.7. The diagnostic spirometry test can have been performed up to three years prior to randomisation, or if never performed before, should be performed not earlier than 4 weeks since last exacerbation
5. Smokers or ex-smokers with a smoking history of >10 pack years (a pack year is defined as 20 cigarettes smoked every day for a year)
6. Clinical diagnosis documented in the patient's medical records of one or more major chronic cardiac disease (heart failure, ischaemic heart disease or atrial fibrillation).
7. Currently receiving at least one of the specified treatments (either alone or in combination, see Appendix 10.5) for heart failure, ischemic heart disease or atrial fibrillation.
8. Participant must be willing and able to perform pulmonary function tests

Sex

9. Male or female. Contraception is not considered necessary in this cohort of elderly (> 60 years) patients receiving treatment with commercially available licensed products.

Informed Consent

10. Capable of giving signed informed consent as described in Appendix 1 which includes compliance with the requirements and restrictions listed in the informed consent form (ICF) and in this protocol.

5.2. Exclusion Criteria

Participants are excluded from the study if any of the following criteria apply:

Medical Conditions

1. Patients with a primary discharge diagnosis of DRG 087 or DRG 088 but clearly judged by the clinical investigator to be due to other causes, i.e. patients presenting to the hospital with symptoms of AECOPD but due mainly to other conditions (pulmonary embolism, pneumonia, pneumothorax, anaemia, acute kidney failure, decompensated heart failure, acute ischemic heart disease, new onset atrial fibrillation, stroke, etc.)
2. Patients who required invasive mechanical ventilation during hospitalization
3. Patients with Asthma as primary and principal diagnosis
4. Patients with severe cardiovascular (CV) disease who in the opinion of the investigator are unlikely to survive the 15 month study period
5. Patients considered unable to comply with the study procedures and follow-up in the opinion of the investigator (eg, evidence of alcohol or drug abuse, psychiatric disorder, physical disability, social or geographical obstacles)
6. Patients in whom spirometry is contraindicated (eg, haemoptysis, detached retina, active tuberculosis, last trimester of pregnancy)
7. Patients with other mechanical or overt causes of respiratory symptoms, particularly dyspnoea (such as pneumothorax, chest wall trauma, lung fibrosis, lung cancer, anaemia, severe obesity (BMI >40) or cachexia (BMI <18))
8. Patients with any major disease which in the opinion of the investigator would prevent study participation, such as dementia, end-stage disease, cachexia, chronically bedridden patient and life expectancy <15 months.

Prior/Concurrent Clinical Study Experience

9. Participation in any other interventional study within the last 3 months or concurrent participation in an observational clinical study

5.3. Lifestyle Considerations

No lifestyle restrictions are required.

5.4. Screen Failures

Screen failures are defined as participants who consent to participate in the clinical study but are not subsequently randomly assigned to study intervention. A minimal set of screen failure information is required to ensure transparent reporting of screen failure participants to meet the Consolidated Standards of Reporting Trials (CONSORT) publishing requirements and to respond to queries from regulatory authorities. Minimal information includes demography, screen failure details, eligibility criteria, and any serious adverse event (SAE).

Individuals who do not meet the criteria for participation in this study (screen failure) can be rescreened at a later date.

6. Study Intervention

Study intervention is defined as any investigational intervention(s), marketed product(s), placebo, or medical device(s) intended to be administered to a study participant according to the study protocol.

6.1. Study Intervention(s) Administered

In this study patients will be randomised to receive one of the following two treatment regimens for up to 12 months:

- 1) Usual and optimized treatment for concomitant cardiovascular (CV) diseases plus inhaled long acting bronchodilator(s) (LABD(s))
- 2) Usual and optimized treatment for concomitant CV diseases plus inhaled long acting bronchodilator(s) and inhaled glucocorticosteroids (ICS).

The choice of the specific LABD(s) and/or ICS for each patient will be left to the discretion of the clinical investigator. All treatments will be administered at licensed dosages. During the study, the doses of all medications may be adjusted by the investigator according to licensed dosages. Both study groups will receive prescriptions for study medication, which will be collected by the patients from their local pharmacy or hospital pharmacy department. Prescription data will be captured on the electronic case report form (eCRF).

6.2. Preparation/Handling/Storage/Accountability

Participants enrolled in the study will receive medication dispensed from the local pharmacy or hospital pharmacy department in the usual way, there are no additional preparation, handling, or storage requirements.

Participants will be requested to bring any unused medication and the used empty device inhalers when they attend for their next visit and the investigator will make an assessment of the participant's compliance with treatment from the quantity of medication returned and by directly asking the participant about their compliance with the prescribed COPD treatment.

6.3. Measures to Minimize Bias: Randomization and Blinding

All participants will be centrally assigned to randomized study intervention using an Interactive Web Response System (IWRS). Before the study is initiated, the log in information and instructions for the IWRS will be provided to each site.

The center will be considered as a unique stratifying factor, so the randomization will follow a balanced-block center-stratified design.

Study intervention will be dispensed at the study visits summarized in the SoA.

This is an open-label study; however, the specific intervention to be taken by a participant will be assigned using an IWRS. The site will contact the IWRS prior to the start of study intervention

administration for each participant. The site will record the intervention assignment on the applicable case report form.

Potential bias will be reduced by using central randomization.

Since this is an open label study, no unblinding procedures are foreseen.

6.4. Study Intervention Compliance

Participants will be instructed in the correct method of using the inhaler device(s) at the randomization visit (Visit 2) and their technique will be checked at each follow-up visit to ensure that they are using the device(s) correctly.

Participants will be requested to bring their medication when they attend for their next visit and the investigator will make an assessment of the participant's compliance with their treatment from the quantity of medication returned, including the empty drug device inhalers and by directly asking the participant about their compliance with their COPD treatment. The investigator will then provide a response to the following question in the eCRF: "Has the subject been compliant with the study medication up to this visit?"

6.5. Concomitant Therapy

Additional therapeutic or diagnostic procedures (i.e. use of concomitant medication) will be performed according to local guidelines (PDTA).

Any medication or vaccine (including over-the-counter or prescription medicines, vitamins, and/or herbal supplements) that the participant is receiving at the time of enrollment or receives during the study must be recorded in the eCRF at each visit. Information recorded will include:

- Name of medication
- Reason for use
- Dates of administration including start and end dates
- Dosage information including dose and frequency

Treatment with ICS in the only LABDs group will be permitted if, on clinical Investigators judgement, it would be necessary for patient temporary conditions for at maximum 15 days in case of patient treated at home or for 15 days (at maximum) after hospital discharge in case of hospitalised patient. If the ICS treatment will surpass these periods, the patient will be considered being switched to the LABD + ICS group and considered as protocol violator.

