7.1. Discontinuation of Study Intervention

Participants who are hospitalized during the study period will be allowed to continue in the study until the end at the discretion of the principal investigator and/or the participant. The investigator/participant can decide to discontinue the study drug for safety or efficacy reasons.

Albeit we will invite patients and doctors to stick to the initial treatment unless required by changed medical condition, the specific COPD treatment regimen (LABD(s) without ICS or LABD(s) + ICS) can be changed at any point during the study. Treatment with ICS in the only LABDs group will be permitted if, on clinical Investigators judgement, it would be necessary for patient temporary conditions for at maximum 15 days in case of patient treated at home or for 15 days (at maximum) after hospital discharge in case of hospitalised patient. If the ICS treatment will surpass these periods, the patient will be considered being switched to the LABD + ICS group and considered as protocol violator.

See the SoA for data to be collected at the time of intervention discontinuation and follow-up and for any further evaluations that need to be completed.

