9.2. Sample Size Determination

The sample size calculation is based on the superiority criteria of the LABD+ICS group vs. LABD alone group in terms of re-hospitalization and/or death. With 464 patients in each group, the percentage of patients experiencing the composite event (re-hospitalization and/or death) is expected to be 9% in the LABD+ICS group and 15% in the LABD alone group. A log-rank test (two-sided 5% significance level) will have 80% power to detect a difference between treatment groups in terms of time to first re-hospitalization and/or death (primary efficacy endpoint). Adjusting for an expected 10% dropout rate, a total of 516 patients per group will need to be randomized.

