9.3. Populations for Analyses

The following populations will be considered for the analysis:

- **Randomized population:** all randomized patients.
- **Safety population:** all randomized patients who receive at least one administration of the study treatment in a given treatment period.
- **Intention-to-Treat population (ITT):** all randomized patients from the safety population with at least one available post-baseline efficacy evaluation during the treatment period.
- **Per-protocol population (PP):** all randomized patients from the ITT population without any major protocol deviations (e.g., wrong inclusions, forbidden concomitant medications, etc.). The exact definition of major protocol deviations will be discussed with the clinical team case by case during the review of the data and will be described in the Data Review Report.

The statistical analysis will be performed after database lock.

The primary efficacy variable will be analysed both in the ITT and in the PP populations. As this is a superiority study, the primary analysis population will be the ITT. All the other efficacy variables will be analysed in the ITT population only.

Analysis of safety variables will be performed on the safety population.

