4.2.4 Per Protocol population (PP)

All randomized patients from the ITT population without any major protocol deviations.

The exact definition of major protocol deviations will be discussed with the clinical team case by case during the review of the data and will be described in the Data Review Report.

The primary efficacy variable will be analysed on the PP.

In case an error occurs in treatment allocation, the following rule will be followed: if a patient was randomised but received the incorrect treatment, he/she will be reported under his/her randomised treatment group for all analyses performed on the ITT population, but he/she will be reported under the treatment actually received for all analyses performed on the safety population. The patient will be excluded from the PP population.

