7.1 Analysis of primary endpoint

Definitions and data conventions

First re-hospitalization and/or death

The event “first re-hospitalization and/or death” is identified as the first occurrence between the first re-hospitalization (as collected in the “COPD EXACERBATION FORM”) and death, if any of them occurred.

Time to first re-hospitalization and/or death

Forms			
Title		Statistical Analysis Plan Template	
Code		Version	Effective Date
FRM_ST03_032		02	02 Oct 2017
			17 of 26

In patients with at least one event, time to first re-hospitalization and/or death will be calculated as the weeks between baseline (Visit 2) and the date at which the first re-hospitalization (i.e., Date of admission/prolonged hospitalization in the ‘COPD Exacerbation Form’) and/or death occurs.

Time to first re-hospitalization and/or death (weeks) = (date of first re-hospitalization and/or death - Visit 2 + 1)/7

Patients without first re-hospitalization and/or death or who are discontinued before having it will be considered as “censored” at the end of the study visit (Visit 6) or at the time of the withdrawal during the treatment period (i.e., the date of withdrawal). For the analysis, the following formula will be applied:

Censoring time (weeks) = (date of Visit 6/withdrawal - Visit 2 + 1)/7

Time to first re-hospitalization and/or death for the sensitivity analysis.

The crossover occurrence is identified as patients that switch from one treatment group to the other adding or stopping ICS and it will be identified as protocol deviation.

In patients without the crossover occurrence , time to first re-hospitalization and/or death will be calculated as described above.

In patients with the crossover occurrence:

- if they experienced first re-hospitalization and/or death before or at the crossover occurrence date, time to first re-hospitalization and/or death will be calculated and considered as for the patients without the crossover occurrence;
- if they experienced first re-hospitalization and/or death after the crossover occurrence date, time to first re-hospitalization and/or death will be censored at the time of crossover occurrence;
- patients without first re-hospitalization and/or death will be considered as “censored” at the cross-over start date. For the analysis, the following formula will be applied:

Censoring time (weeks) = (date of cross-over start - Visit 2 + 1)/7

Primary efficacy analysis

Analysis will be performed on ITT population.

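### The Per Protocol analysis can remove LABD-arm patients together with a completed primary event, because of ICS continued after that event

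*Protocol*

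**What the plan says.** **The ICS limit.** Protocol 6.5 and 7.1 allow temporary ICS in the LABD arm for up to 15 days at home, or "for 15 days (at maximum) after hospital discharge in case of hospitalised patient". If the limit is passed, "the patient will be considered being switched to the LABD + ICS group and considered as protocol violator". Neither section asks whether the primary event has already happened. Protocol 7.1 also lets hospitalised participants stay in the study, and 6.5 requires start and stop dates for all medication, so ICS use after an event will be on record.

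**The crossover rule.** SAP 7.1 defines crossover as adding or stopping ICS and says that "it will be identified as protocol deviation". For the crossover sensitivity analysis it keeps first events that fall on or before the switch date and censors at the switch otherwise.

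**The PP set.** Protocol 9.3 defines PP as ITT patients "without any major protocol deviations (e.g., wrong inclusions, forbidden concomitant medications, etc". Both documents leave the exact meaning of major to a case-by-case discussion at data review. SAP 4.2.4 adds: "The primary efficacy variable will be analysed on the PP". No timing condition is attached to deviations.

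**The primary analysis.** Protocol 9.3 and SAP 4.2.3 make ITT the primary set.

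**The concern.** The after-discharge branch of the ICS limit applies only to someone who has been in hospital. Under the protocol's all-cause definition, the first admission after Visit 2 is the primary event. A LABD patient admitted in month 4 has completed the endpoint. If ICS then runs more than 15 days past discharge, the patient becomes a violator and may be removed from PP with the month-4 event, although later ICS cannot have affected it. A LABD+ICS patient with the same admission who simply continues ICS breaches nothing and stays in.

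Through this route, PP membership depends on the outcome and on the arm. PP is the second planned analysis of the primary endpoint. A real benefit could be diluted there by selection alone, and the ITT and PP results could seem to disagree. The SAP already applies the right principle in its crossover analysis, so the same patient could count as an event in one supporting analysis and be missing from the other.

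**Working it through.** **Inputs.** From Protocol 9.2: the composite event "is expected to be 9% in the LABD+ICS group and 15% in the LABD alone group", 464 evaluable patients per arm, two-sided 5% level, 80% power, 10% dropout. Assumption, not in the documents: f, the share of LABD event patients removed from PP because ICS continued after the event.

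**The plan's own figure.** Under proportional hazards, HR = ln(0.91)/ln(0.85) = 0.580. Freedman's formula gives 7.849 × (1.580/0.420)² ≈ 111.3 events. Dividing by 0.15 + 0.09 = 0.24 gives 464 per arm, as stated, and 464/0.90 rounds up to 516. Expected events are 464 × 0.15 = 69.6 and 464 × 0.09 = 41.8.

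**This route alone, with no other exclusions.**
- LABD risk in PP = 69.6(1 − f) / (464 − 69.6f)
- PP HR = ln(0.91) / ln(1 − LABD risk)

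| f | LABD events | LABD patients | LABD risk | PP HR |
|---|---|---|---|---|
| 0 | 69.6 | 464.0 | 15.0% | 0.58 |
| 10% | 62.6 | 457.0 | 13.7% | 0.64 |
| 20% | 55.7 | 450.1 | 12.4% | 0.71 |
| 30% | 48.7 | 443.1 | 11.0% | 0.81 |
| 40% | 41.8 | 436.2 | 9.6% | 0.94 |
| 50% | 34.8 | 429.2 | 8.1% | 1.12 |

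The HR reaches 1 when 0.15(1 − f)/(1 − 0.15f) = 0.09, so f = 0.06/0.1365 = 44%.

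Approximate power is Φ(|ln HR| × √(D/4) − 1.96), where D is total events. It falls from 82% (D = 111.4) to 38% at f = 20% (D = 97.4) and 17% at f = 30% (D = 90.5). A simulated Cox analysis with 464 per arm and 400 runs per scenario agrees: HR 0.70 and 0.81, power 39% and 16%, and HR 0.98 at f = 44%.

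**With other exclusions.** Let g be the share of event-free LABD patients removed (for example through the 15-day home limit) and h the share of LABD+ICS event patients removed (for example for stopping ICS). The LABD risk becomes 0.15(1 − f)/[0.15(1 − f) + 0.85(1 − g)], and the LABD+ICS risk becomes 0.09(1 − h)/[0.09(1 − h) + 0.91].

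| f | g | h | PP HR |
|---|---|---|---|
| 20% | 10% | 0 | 0.65 |
| 20% | 20% | 0 | 0.58 |
| 10% | 20% | 0 | 0.52 |
| 20% | 0 | 20% | 0.58 |
| 20% | 0 | 40% | 0.44 |

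The distortion can therefore go either way or cancel.

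**The case against.** A reader might infer that the PP analysis will drop control-arm events only, and so will push the hazard ratio towards or past 1. The documents do not support that, for these reasons.

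- **Exclusion is possible, not prescribed.** The ICS sections say violator and SAP 7.1 says deviation; neither says major. Protocol 9.3 does name forbidden concomitant medication as an example, but ICS in the LABD arm is allowed within limits, and Protocol 7.1 lets the regimen change at any time. Data review could class a post-event switch as not major.
- **The control arm is not the only one exposed.** SAP 7.1 treats stopping ICS as a deviation too, so a LABD+ICS patient who stops after an admission can also leave PP. Only the day limit is one-sided.
- **The direction is not settled.** The home limit can remove event-free LABD patients. Passing 1 needs about 44% of LABD event patients removed with no offset, and a patient whose first event is death cannot leave this way.
- **The link from discharge to event is not complete.** The limit could also be read to cover ICS carried over from the index admission, which is not a primary event. SAP 7.1 takes re-hospitalisations from the COPD Exacerbation Form, so not every later admission is clearly an event under the SAP.
- **Success does not rest on PP.** The claim rests on ITT, and the crossover analysis already keeps pre-switch events.

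All five stand, and they limit the claim. They do not remove the gap. Leaving the decision to data review is weak protection in an open-label trial where SAP 4.9 places that meeting after database lock. SAP 5.1 does not list PP among the sets to be counted, and SAP 5.2 plans no summary of violations, so selective exclusion would be hard to see.

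A further objection concerns the remedy. If only pre-event deviations exclude, event-free patients have the whole year in which to be removed and event patients only part of it. With LABD-arm switching unrelated to outcome, g = 20% and f of about 10% give HR 0.52. That is correct, and it is why the fix below uses censoring.

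**Conclusion.** The concern holds in limited form. As written, the plan permits a LABD patient to be removed from PP, with a completed primary event, for ICS use that followed it. Nothing in the PP definition prevents this, and the day limit that triggers it exists in one arm only.

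Through this route alone the PP hazard ratio rises from 0.58 to 0.64–0.81 for 10–30% of LABD event patients removed. Those figures rest on the planned 15% and 9%, proportional hazards, an assumed share and no offsetting exclusions. The net direction in the real PP set cannot be determined from the documents. Selecting patients on something that happens after the endpoint is unsound whichever way it pushes. The ITT primary analysis and its success criterion are unaffected.

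**What to change.** Add to SAP 4.2.4 and Protocol 9.3, for both arms and before data review:

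1. For the primary endpoint, a deviation that starts after the patient's first primary event is not a reason for exclusion from PP.
2. A patient who adds or stops ICS before any primary event stays in the randomised arm and is censored at the switch date, as in the SAP 7.1 crossover analysis, rather than being removed.

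The second sentence is needed. In simulation, excluding pre-event switchers left a smaller bias in the opposite direction (HR 0.52 to 0.57 against a true 0.58), while censoring at the switch returned 0.58. Censoring does assume that switching is unrelated to prognosis, an assumption the planned crossover analysis already makes; the report should say so.

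The cost is one or two sentences and a date comparison when deviations are classified, using dates already collected. The clinical rule on ICS use is not changed.
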